17 Central venous to arterial CO₂ partial pressure difference (AVCO₂) measures the circulatory clearance of
18 tissue CO₂ and has been proven to be correlated with CO in critically ill adult patients⁵. Widening of AVCO₂
19 represents an imbalance between CO₂ clearance by CO and tissue CO₂ production. With limited data available,
20 it remains unknown whether AVCO₂ is a useful adjunctive marker for assessment CO adequacy in pediatric
21 patients after cardiac surgery with CPB.

22 Additionally, increase cytokine production both pro- (interleukin (IL)-6, IL-8, and tumor necrotic factor
23 (TNF)- α) and anti-inflammatory cytokines (IL-4, IL-10) caused by CPB-induced inflammatory activation can
24 alter multiorgan function and vascular permeability. The relationship between level of these cytokines and
25 clinical outcomes also remains uncertainty in children population.

26 We aimed to evaluate the association between AVCO₂ and inflammatory markers at 4 different time points
27 post operatively with LCOS-related poor outcome and calculate predictability of these markers to facilitate
28 earlier recognition and management LCOS in children undergone cardiac surgery with CPB.

29 30 7. Objective(s) of the study

31 **Main or Primary objective:** To compare accuracy of prediction of LCOS-related poor outcome between
32 AVCO₂ and traditional bedside surrogates (lactate, ScvO₂ and AVO₂) in children with cardiac disease who
33 undergone CPB.

[figure not shown]
34 **Secondary objectives:**

1 7.1 To evaluate association between AVCO_2 in children with cardiac disease who undergone CPB and other
 2 morbidities: 28-ventilator free day, 28-ICU free day, acute kidney injury, and deaths from any cause during
 3 hospitalization.

4 7.2 To evaluate association between level of pro- and anti-inflammatory cytokine in children who underwent
 5 CPB and LCOS-related poor outcome.

6

7 **8. Conceptual framework**

8

9 **9. Literature review**

10 AVCO_2 difference

11 A retrospective study done by Rhodes LA, et al³ evaluated correlation of AVCO_2 with other cardiac output
 12 surrogates (lactate, ScvO₂ and AVO₂) and its capacity to predict poor outcomes associated with LCOS in 139
 13 infants who underwent CPB. There were only 24.5% of poor outcome in this study. The results showed moderate
 14 correlation between AVCO_2 difference with AVO₂ ($R^2 = 0.53$; $p < 0.01$), and ScvO₂ ($R^2 = -0.43$; $p < 0.01$), but not

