15	Where: Sensitivity (p)	= 0.85
16	Precision (d); not more than 10% of p	= 0.09
17	Alpha	= 0.05

18 We applied the sensitivity of lactate > 3 mmol/L for major morbidity, which defined as at least one of
19 complications (i.e., neurological, pulmonary, gastroenteric, and need for extracorporeal membranes oxygenation or
20 ventricular-assist device, or sepsis)¹⁶.

21 Estimated patient (n_0) is 61 cases. Based on 48% of incidence of LCOS-related outcome last year in our
22 study setting, the required total sample size including non-disease and disease participants will be 128 (=61/0.48).

23 Regarding with our sample size calculation for two objectives and an estimate of 20% of unusable data
24 from a sample of 128 participants has been considered. The final sample size is 154 participants for sensitivity of
25 0.85. However, we will collect blood sample for inflammatory markers in 32 patients for preliminary analysis.

26 **9.6. Variables of the study**

27 9.6.1. Dependent variable: poor outcomes indirectly represented from low cardio output syndrome

28 - LCOS-related poor outcome is modified from the study of Drennan SE, et al and Carmona, et al^{14, 15}
29 which consisting of at least two of the following criteria within 48 hour post operatively:

- 1 a. Clinical findings suggestive of LCOS: prolonged capillary refill > 3 s, systolic blood pressure < 5th
2 percentile for age and gender, persistently elevate of LA pressure above 10 mmHg for at least 6 hr
3 , low urine output (< 1mL/kg/hr) for at least 6 hour despite diuretic use
- 4 b. Laboratory findings suggestive of LCOS: persistently elevated lactate (>2 mmol/L), metabolic
5 acidosis with an increase in the base deficit (>4 mmol/L) for at least 6 hr consecutively.
- 6 c. Vasoactive-inotropic score (VIS) \square 20
- 7 d. Any unplanned surgical reinterventions, cardiac arrest, or utilization of extracorporeal membrane
8 oxygenator (ECMO) within 48 hours
- 9 e. Left ventricular fraction less than 50% by echocardiography

10 The LCOS-related outcome will include both anatomical LCOS and physiological LCOS that caused by

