11 CPB

[figure not shown]
- 12 - Vasoactive-Inotropic Score (VIS) based on Belletti A, et al¹⁷ which is summation of dopamine dose
13 (mcg/kg/min) + dobutamine dose (mcg/kg/min) + 100 x epinephrine dose (mcg/kg/min) + 10 x milrinone
14 dose (mcg/kg/min) + 100 x norepinephrine dose (mcg/kg/min) + 10000 x vasopressin dose (U/kg/min)
15 + 50 x levosimendan dose (mcg/kg/min) + 20 x methylene blue dose (mg/kg/h) + 10 x phephylephrine
16 dose (mcg/kg/min) + 10 x terlipressin dose (mcg/min) + 0.25 x angiotensin II dose (ng/kg/min)
- 17 - Acute kidney injury (AKI) based on KDIGO guideline 2012¹⁸ defined AKI as any of following: increased
18 in SCr by \square 0.3 mg/dL within 48 hours, or increased in SCr to \square 1.5 times baseline, which is known
19 or presumed to have occurred within the prior 7 days, or urine volume < 0.5 mL/kg/h for 6 hours
- 20 - 28 ventilator free day (VFDs) and 28 ICU free day (IFDs): the number of days those patients were alive
21 and free from invasive ventilator or ICU stay within 28 days by counting the day of first operative night
22 as the first day. VFDs and IFDs will be counted as zero in non-survivor patients.

23 9.6.2. Independent variables: AVCO₂, ScvO₂, lactate, inflammatory markers at 0, 6, 12, and 24 hour after
24 operation with additional inflammatory markers at pre-operative stage

25 9.6.3. Potential confounder variables: age, gender, risk stratification for cardiac surgery (RACHS score),
26 nutritional status, duration of bypass time or aortic clamp time

27 9.6.4. Methods to minimize bias during study: we will blind the result of inflammatory markers to attendant
28 physician by sending blood sample to research lab which will not be reported in HIS system. Blood
29 sample collection and processing time will be fixed to ensure laboratory quality of the specimen and
30 its interpretation.

31 32 **9.7. Study procedure(s)/stage(s)**

1. Researcher will introduce research project verbally to cardiac pediatrics patient or their legal guardians at cardiac outpatient clinic when he/ she are scheduled to have cardiopulmonary bypass surgery at Songklanagarind Hospital. Researcher will later request patient or legal guardians to sign the informed consent when he/she is admitted in hospital 24 hours in advance.

2. If patient has already been admitted in hospital for any reason and have schedule for surgery, researcher will inform patient or legal guardians 48 hours in advance.

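### Lactate is both a compared test and part of outcome criterion b, which tilts the AVCO₂-versus-lactate comparison towards lactate; no visible line of section 9.11 removes it

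*Combined protocol and SAP*

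**What the plan says.** Section 7 names the tests and population of the primary comparison: "AVCO₂ and traditional bedside surrogates (lactate, ScvO₂ and AVO₂) in children with cardiac disease who" had bypass surgery. Section 9.6.2 lists the predictors and their times: "9.6.2. Independent variables: AVCO₂, ScvO₂, lactate, inflammatory markers at 0, 6, 12, and 24 hour after" surgery.

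Section 9.6.1 defines the outcome as at least two of criteria a to e within 48 hours. Criterion b reads "Laboratory findings suggestive of LCOS: persistently elevated lactate (>2 mmol/L), metabolic" and continues "acidosis with an increase in the base deficit (>4 mmol/L) for at least 6 hr consecutively". Only a comma separates the lactate and base-deficit parts, so it is not stated whether one or both are needed, or whether the 6-hour duration applies to lactate. Criterion c is a threshold on the vasoactive-inotropic score (VIS). AVCO₂, ScvO₂ and AVO₂ appear in no criterion.

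Section 9.11 plans accuracy indices for the primary objective, ROC areas, a Cox model, one sensitivity analysis (physiological LCOS) and one subgroup analysis (univentricular versus biventricular repair). On the first of these last two, section 9.6.1 says "The LCOS-related outcome will include both anatomical LCOS and physiological LCOS that caused by" bypass; a figure next to that text could not be read here. Section 9.6.4 blinds clinicians to the inflammatory markers only.

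Objective 7.1 is "To evaluate association between AVCO_2 in children with cardiac disease who undergone CPB and other" morbidities: ventilator-free days, ICU-free days, kidney injury and death. None of these contains lactate, but the objective concerns AVCO₂ alone.

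**The concern.** When a test helps to define the condition it is meant to predict, its accuracy is inflated (incorporation bias). Here this happens to one side of the primary comparison only. All four lactate test times fall inside the 48-hour outcome window, so lactate receives credit that AVCO₂ cannot receive.

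The protocol argues in sections 6 and 10.3 that lactate and the other usual surrogates have limitations and that AVCO₂ may help. The bias works against that hypothesis. If AVCO₂ comes out ahead of lactate, the result stands despite the bias. If the two look alike, or lactate looks better, the reader cannot tell whether AVCO₂ adds nothing or lactate was helped by the definition. Enrolling more patients would not resolve this.

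**Working it through.** **The plan's own figure.** Section 9.5 takes sensitivity 0.85, precision 0.09, alpha 0.05, incidence 0.48 and 20% unusable data.

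- n₀ = 1.96² × 0.85 × 0.15 / 0.09² = 60.5, rounded up to 61.
- 61 / 0.48 = 127.1, rounded up to 128.
- 128 × 1.2 = 153.6, rounded up to 154.

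All three reproduce. None bears on the outcome definition.

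**Is there overlap?** Lactate is a test (sections 7 and 9.6.2) and an element of criterion b (9.6.1). The documents do not say which samples decide b. Section 9.7 describes routine arterial gases every 2 to 6 hours, so partial overlap with the test samples is likely; that is an inference.

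**How large could the bias be?** The documents give no frequency for any criterion, so this needs a model with assumed inputs. Each patient has a latent severity S.

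- AVCO₂, test lactate, criterion lactate and base deficit each equal ρS + √(1−ρ²) × error, with ρ = 0.4. The two tests are therefore equally good by construction.
- The errors of test lactate and criterion lactate correlate 0.5 to 0.7.
- The errors of base deficit and criterion lactate correlate 0 or 0.3.
- The lactate part of b has prevalence 0.5, the base-deficit part 0.3 or 0.5.
- Criteria a, c, d and e load 0.7 on S. Their thresholds are shifted together so that two-of-five has incidence 0.48, assuming the section 9.5 figure used this definition.
- A wider grid uses ρ = 0.3 and 0.5 and base-deficit error correlation up to 0.6.

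AUC(lactate) minus AUC(AVCO₂), where the true difference is zero:

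| Outcome | Lead for lactate |
|---|---|
| Full definition, b = lactate OR base deficit | 0.029–0.073; wider grid 0.028–0.086 |
| Full definition, b = lactate AND base deficit | 0.015–0.054; wider grid 0.015–0.073 |
| b on base deficit only, error correlation 0 | 0.00 |
| b on base deficit only, error correlation 0.3 (wider grid) | 0.014–0.028 |
| b on base deficit only, error correlation 0.6 | 0.027–0.055 |
| b removed, lactate and VIS errors independent | at most 0.002 |
| b removed, lactate–VIS error correlation 0.1–0.4 | 0.012–0.056 |

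A simpler model, with b driven by lactate alone and not calibrated to 48%, gave 0.03 to 0.12 as the correlation between test and criterion lactate errors rose from 0.3 to 0.9. For scale, the infant study in the literature review reports AUCs of 0.69 for AVCO₂ and 0.64 for lactate, a gap of 0.05.

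**What removing b costs.** In the main grid, incidence with b removed is 0.261–0.302 (OR) or 0.398–0.444 (AND). Any patient with two of the remaining four criteria also meets two of five, so the share of cases that depend on b is (0.48 − incidence) / 0.48:

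- OR: (0.48 − 0.302) / 0.48 = 37% to (0.48 − 0.261) / 0.48 = 46%.
- AND: (0.48 − 0.444) / 0.48 = 8% to (0.48 − 0.398) / 0.48 = 17%.

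The half-width for sensitivity 0.85 is 1.96 × √(0.85 × 0.15 / events), with 128 evaluable patients:

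- Full definition: 128 × 0.48 = 61.4 events, 0.089.
- b removed, OR: 33.4 to 38.7 events, 0.121 to 0.113.
- b removed, AND: 50.9 to 56.8 events, 0.098 to 0.093.

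With b on base deficit only, incidence is 0.378–0.424 (OR) or 0.507–0.548 (AND).

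**The case against.** The best defence is that b alone never makes a case, that lactate is a reasonable element of an LCOS definition, and that AVCO₂ is offered as an adjunct with no formal superiority or non-inferiority claim. The first point dilutes the bias but does not remove it, and the simulations already apply the two-of-five rule. The second is a reason to keep the full definition, not to rely on it alone. The third lowers the stakes, but the primary objective is still a head-to-head comparison of accuracy.

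It is also fair to say that the size rests on correlations with no source in the documents. The direction of the incorporation effect does not depend on them.

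Several stronger readings are tempting and are not supported:

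- That dropping lactate gives a clean comparison. Base deficit may track lactate. Section 6 itself names beta-adrenergic agonists as a cause of raised lactate, and VIS, which is criterion c, sums such drugs. The near-zero bias with b removed holds only if lactate and VIS errors are independent.
- That only the traditional markers are visible to clinicians. Section 9.6.4 blinds inflammatory markers alone, so AVCO₂ is visible too.
- That incorporation distorts the ScvO₂ and AVO₂ comparisons. Neither is in any criterion; influence through treatment is a separate matter.
- That 9.11 certainly contains no lactate-free analysis. The physiological-LCOS analysis appears to select patients rather than remove lactate, but the unread figure leaves some doubt.
- That a true AVCO₂ lead would be reversed. Without criterion frequencies this cannot be shown.

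**Conclusion.** The concern holds as incorporation bias in the AVCO₂-versus-lactate comparison, directed towards lactate, with no visible analysis that removes it. Under assumed inputs calibrated to 48% incidence, the spurious AUC lead is about 0.03–0.09 (OR reading of b) or 0.015–0.07 (AND reading), which is of the same order as the 0.05 gap in the cited infant study.

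The remedies reduce the bias and do not abolish it. Base deficit only keeps about 0 to 0.05 AUC in lactate's favour as the assumed error correlation goes from 0 to 0.6. Removing b ends direct incorporation but can leave about 0.01–0.06 if lactate and VIS errors correlate 0.1–0.4, through the drugs themselves or through clinicians acting on visible values. This is a cheap improvement worth making before the outcome is analysed; it does not invalidate the design.

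**What to change.** In section 9.11, prespecify that the comparison of all four tests is repeated beside the full definition on two derived outcomes:

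- Main sensitivity analysis: criterion b removed, requiring two of the remaining four criteria.
- Supporting sensitivity analysis: criterion b met on base deficit only.

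Report how many cases qualify only through b. State the residual bias of each analysis. State that the full definition alone will not be used to conclude that AVCO₂ is no better than lactate.

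In section 9.6.1, state whether criterion b needs one or both parts and whether the 6-hour duration covers lactate. In section 11, note that only inflammatory markers are blinded, so lactate, ScvO₂, AVO₂ and AVCO₂ are all visible and may influence VIS.

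The cost is two derived variables and a few sentences, with no new data. Two downsides should be stated. Precision falls with b removed: about 33–57 events among 128 evaluable patients and a half-width of about 0.12–0.09, against the planned 0.09. The target condition also changes: removing b turns cases that qualified only through it into non-cases, and base deficit only broadens the outcome if b is read as requiring both parts. For that reason both analyses accompany the full definition and do not replace it.

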11 CPB

[figure not shown]
- 12 - Vasoactive-Inotropic Score (VIS) based on Belletti A, et al¹⁷ which is summation of dopamine dose
13 (mcg/kg/min) + dobutamine dose (mcg/kg/min) + 100 x epinephrine dose (mcg/kg/min) + 10 x milrinone
14 dose (mcg/kg/min) + 100 x norepinephrine dose (mcg/kg/min) + 10000 x vasopressin dose (U/kg/min)
15 + 50 x levosimendan dose (mcg/kg/min) + 20 x methylene blue dose (mg/kg/h) + 10 x phephylephrine
16 dose (mcg/kg/min) + 10 x terlipressin dose (mcg/min) + 0.25 x angiotensin II dose (ng/kg/min)
- 17 - Acute kidney injury (AKI) based on KDIGO guideline 2012¹⁸ defined AKI as any of following: increased
18 in SCr by \square 0.3 mg/dL within 48 hours, or increased in SCr to \square 1.5 times baseline, which is known
19 or presumed to have occurred within the prior 7 days, or urine volume < 0.5 mL/kg/h for 6 hours
- 20 - 28 ventilator free day (VFDs) and 28 ICU free day (IFDs): the number of days those patients were alive
21 and free from invasive ventilator or ICU stay within 28 days by counting the day of first operative night
22 as the first day. VFDs and IFDs will be counted as zero in non-survivor patients.

23 9.6.2. Independent variables: AVCO₂, ScvO₂, lactate, inflammatory markers at 0, 6, 12, and 24 hour after
24 operation with additional inflammatory markers at pre-operative stage

25 9.6.3. Potential confounder variables: age, gender, risk stratification for cardiac surgery (RACHS score),
26 nutritional status, duration of bypass time or aortic clamp time

27 9.6.4. Methods to minimize bias during study: we will blind the result of inflammatory markers to attendant
28 physician by sending blood sample to research lab which will not be reported in HIS system. Blood
29 sample collection and processing time will be fixed to ensure laboratory quality of the specimen and
30 its interpretation.

31 32 **9.7. Study procedure(s)/stage(s)**

1. Researcher will introduce research project verbally to cardiac pediatrics patient or their legal guardians at cardiac outpatient clinic when he/ she are scheduled to have cardiopulmonary bypass surgery at Songklanagarind Hospital. Researcher will later request patient or legal guardians to sign the informed consent when he/she is admitted in hospital 24 hours in advance.

2. If patient has already been admitted in hospital for any reason and have schedule for surgery, researcher will inform patient or legal guardians 48 hours in advance.

3. Preoperative blood sample 1.5 mL will be collected for inflammatory markers level at the same time when patient has intravenous access preparing for NPO or other preoperative blood sample.

4. Patient goes on open heart cardiac surgery and will be admitted directly to pediatric intensive care unit (PICU) for postoperative care.

5. Blood sample for blood gas 0.3 mL for each central line catheter and arterial line catheter and inflammatory markers 1.5 mL drawn from arterial line will be collected at 0, 6, 12, and 24 hours after PICU arrival. Arterial and venous blood gas are accepted if samples are collected within 5 minutes of each other. We allow time gap for collecting blood +/- 1 hr from schedule due to unpredictable ICU occupy.

6. Attending physician provides standard care for post cardiac operation. The decision of treatment by attending physician will not be involved by researchers. Inflammatory markers results will be reported after patient is discharged from hospital to minimize influence of result to physician's decision on treatment.

1 7. Cardiologist will perform echocardiography to evaluate left ventricular function and anatomical defect
 2 that could mimic signs of LCOS within 48 hours postoperatively.

3 8. Researcher prospectively collects postoperative variables including hemodynamic variables and
 4 therapeutic interventions and patient's outcome.

5 9. The primary study endpoint is poor outcome related to LCOS. The secondary endpoints are 28-day
 6 ventilator free day, ICU free day, deaths and correlation of AVCO₂ with other cardiac output surrogates
 7 (AVO₂, ScvO₂ and arterial blood lactate).

8 10. If either central line or arterial line catheter are displaced before 24-hour, remaining data will be
 9 recorded as missing data.

10 **Describe procedures/process of the study. Show how research methodology in the study is different from
 11 the routine practice?**

Processes which are routine practice	Processes which are research
1. Pre-operative lab sampling; CBC, Coagulogram, electrolyte, group match for blood component	1. Adding inflammatory markers to pre-operative lab
2. Serial ABG sampling q 2-6 hr depend on severity of patient	2. Extra 2 blood sampling for VBG (0.3 mL each)
3. Serial VBG sampling q 24 hr	3. Mandatory blood sampling q 6 hr x 5 times for inflammatory markers (1.5 mL each)

12 **9.8. Study instrument(s) and outcome measurement(s)**

- Blood sample for blood gas analysis 0.3 mL will be drawn from arterial line and central venous catheter each with different time less than 5 minutes. The arterial and venous gas will be analyzed by ABL800 Basic (Radiometer, Copenhagen, Denmark) which is located in PICU
- Blood sample for inflammatory markers 1.5 mL will be collected into 3 mL vacutainers without anticoagulant. Collected blood will be kept on room temperature and sent to division of immunology and virology within 3 hours after collecting. Samples will be centrifuged at 500 x g for 15 minutes at 4°C. Supernatant will be transferred to a clean polypropylene tube. Separated serum will be aliquoted into cryogenic vial and stored at -80°C until analysis.
- Serum cytokines (TNFα, IL-1β, IL-6, IL-8, IL-10) will be quantified in serum using multiplex immunoassays (Bio-Plex Pro Human Screening Panel 5plex XPLEX, Bio-Rad, California, USA). The plate will be read on Bio-Plex®200 array reader (Bio-Rad, California, USA) and analyzed using Bio-Plex Manager™ software. Sample will be run in duplicates and cytokine level will be quantified via comparison to standard curve.

1 **9.9. Data collection methodology**

2 - Data record form consists of 5 parts: patient's profile, characteristic of cardiac disease, intra- and post-
3 operative intervention, laboratory values at 4 different time points, and PICU outcome. Researcher will
4 collect data via electronic medical records, nursing record form, and blood gas record sheet of each
5 participant.

6 **9.10. Data management**

7 - All of data will be collected in record form before putting in Epidata program. Study codes will be used on data
8 collection and data document instead of hospital number of patients.

9 **9.11. Statistical analysis**

10 Descriptive part:

11 - For continuous data (i.e., AVCO₂, ScvO₂, lactate, inflammatory markers, and others), we will use mean
12 (\pm SD) in normal distribution and median (\pm IQR) in non-normal distribution. We will use percentages for
13 categorical data (i.e., LCOS-related poor outcome).

14 Analytic part:

15 - Two means of the continuous outcomes will be compared using t-test or Mann Whitney U test. Two or
16 more proportions of the categorical outcomes will be compared using Chi-square or Fisher-exact test.
17 - We will apply the pairwise correlation analysis among independent variables: AVCO₂, lactate, ScvO₂,
18 inflammatory markers with time lagged factor.
19 - For primary objective, we will calculate and compare the accuracy of prediction of LCOS-related poor
20 outcome between AVCO₂ and traditional bedside surrogates, using diagnostic test indices (i.e., sensitivity,
21 specificity, predictive values).
22 - According to secondary objectives, Cox proportional hazard model will be conducted to examine the
23 association between LCOS-related outcomes and other variables. Potential confounders (i.e., age, gender,
24 RACHS score, nutritional status, duration of bypass time or aortic clamp time) were included in the initial
25 model. Then, backward stepwise refinement was performed. Statistical significance was considered when
26 the p-value is less than 0.05.
27 - Area under the Receiver Operating Characteristic (ROC) to evaluate predictability of AVCO₂ compare with
28 other parameters.
29 - Sensitivity analysis in patient who has physiological LCOS-related outcome.
30 - Subgroup analysis between children who undergone univentricular repair and biventricular repair

32 **10. Ethical consideration**

33 **10.1. Possible risks/effects in the study, including preventive and alleviation measures**

34 - According to protocol of this study, the patients might be at risk of infection from collecting blood from
35 arterial line and central venous catheter. However, expertise ICU nurses practically perform blood

1 collection in sterile technique. If patient develops catheter-related blood stream infection, empirical
2 antibiotics will be given immediately.

3 - Patient will be at risk of anemia. According to Ethics committee guideline, amount of blood drawn from
4 patient will not be over the maximum volume for patient's body weight and patient's Hb must be more
5 than 10 g/dL at the time of blood drawing. Packed red cell will be given if patient's Hb is less than 10
6 g/dL in standard care

7 **10.2. Describe the process/ system for assuring confidentiality and the privacy of the research
8 participants/communities**

9 Study codes will be used on data collection and data document instead of hospital number. Subject
10 information will be stored securely in the computer and only researcher can access through data.

11 **10.3. Benefits of the study for participants and the community/country including how findings of the
12 study use for strengthening community.**

13 Since there are limitation of using traditional bedside surrogates (serum lactate, ScvO₂ and AVO₂) to
14 predict LCOS in children who undergone CPB, this new bedside surrogate (AVCO₂) might be another
15 bedside tool to detect post-operative LCOS earlier in order to improve outcome.

16 **10.4. Informed consent process: Process/method of invitation the participants to participate in the
17 research, such as personal contact, referral from other(s), brochure, and announcement, etc.**

18 - Researcher will introduce research project verbally to cardiac pediatrics patient or their legal
19 guardians at cardiac outpatient clinic when he/she are scheduled to have cardiopulmonary bypass
20 surgery at Songklanagarind Hospital and give consent form to legal guardians to sign. Researcher
21 will later request collect the inform consent when he/ she is admitted in hospital 24 hours in
22 advance.

23 - If patient has already been admitted in hospital for any reason and have schedule for surgery,
24 researcher will inform patient or legal guardians 48 hours in advance.

25 **10.5. Procedure specifying for research participant withdrawal from the study**

26 - Blood sample taking will be ceases immediately after participant/legal guardians withdrawn from
27 the study

28 - Data collected from a withdrawn patient will be used in the study analysis. Data after patient
29 withdraw will be inserted as missing data.

30 **10.6. Clearly indicate person(s) responsible for payment for treatment of complications and adverse
31 effects**

32 There is no any intervention or therapeutic trial in this study.

33 **10.7. Compensation for research participant**

34 Yes, please provide detail:.....

1 ✓ No, please provide reasons: patient does not have to spend extra time or any effort during the
 2 research, so there is no compensation will be provided in this study

3 **10.8. Does the study involve biological specimen collection? If yes, also explain how the investigator
 4 manages the leftover specimen.**

5 The study will collect additional total 8.1 mL of blood for inflammatory mediators (1.5 mL each x 5
 6 times for inflammatory markers and extra blood sampling 0.3 mL x 2 times for VBG analysis during
 7 study period). After complete analysis, leftover specimen will be discarded immediately.

8 **10.9. Research project with special ethical consideration (if applicable)**

9 **11. Limitation(s) and barrier(s) of the study (if applicable) and plans for mitigation**

10 - The time of blood sampling might be inaccurate as schedule. The protocol allows the time gap 1 hour from
 11 schedule to be more flexible for ICU nurse.

12 **12. Time schedule of the study**

13 Duration of the study: From August 2021 to April 2023 Total time: 21 months

Activity	Jun-Dec 2021	Jan-Dec 2022	Jan-Sep 2023
1. Proposal submission for EC	Jun-Aug 2021 ➡		
2. Data collection		Aug 2021 – Apr 2023 ➡	
3. Data analysis			Jan-Apr 2023 ➡
4. Manuscript writing			Apr-Jun 2023 ➡
5. Presentation to faculty			Sep 2023 ➡

15 **13. Budget detail of the study**

16 ✓ Funded by: Research fund, Faculty of Medicine, Prince of Songkla University

17 Budget amount:

18 Expecting funded from:

19 Budget amount:

20 Private fund

21 Budget amount:

Cost category	Cost
Payment for laboratory technician who centrifuge blood sample as protocol 20 baht/1 blood sample	3,200 baht

= 20 baht x 5 times x 20 participants	
Equipment Multiplex immunoassays (Bio-Plex Pro Human Screening Panel 5plex XPLEX, Bio-Rad, California, USA) = 87,205 x 2 plate	174, 410 baht
Grand total	177,610 baht

1

2 **14. Expected outcomes of the study**

3 Publication in international journal (Scopus, pubmed) and oral/poster presentation in international conference.

4 **15. References**

5 1. Shekerdemian L. Perioperative manipulation of the circulation in children with congenital heart disease. *Heart.* 2009;95(15):1286-96.

6 2. Wernovsky G, Wypij D, Jonas RA, et al. Postoperative course and hemodynamic profile after the arterial switch operation in neonates and infants. A comparison of low- flow cardiopulmonary bypass and circulatory arrest. *Circulation.* 1995;92(8):2226-35.

7 3. Rhodes LA, Erwin WC, Borasino S, et al. Central venous to arterial CO₂ difference after cardiac surgery in infants and neonates. *Pediatr Crit Care Med.* 2017;18(3):228-33.

8 4. Moussa MD, Durand A, Leroy G, et al. Central venous- to-arterial PCO₂ difference, arteriovenous oxygen content and outcome after adult cardiac surgery with cardiopulmonary bypass: A prospective observational study. *Eur J Anesthesiol.* 2019;36(4):279-89.

9 5. Lamia B, Monnet X, Teboul JL. Meaning of arterio-venous PCO₂ difference in circulatory shock. *Minerva Anestesiol.* 2006;72(6):597-604.

10 6. Furqan M, Hashmat F, Amanullah M, Khan M, Durani HK, Haque A. Venoarterial PCO₂ difference: a marker of postoperative cardiac output in children with congenital heart disease. *J Coll Physicians Surg Pak.* 2009;19:640-3.

